8.3.3. Special Assessments of Potential Hepatotoxicity

The number and percentage of subjects who met the criteria in [Table 14](#), based on their maximum post-baseline value, will be presented to assess any potential for drug-induced hepatotoxicity or liver injury per Guidance for Industry: Drug Induced Liver Injury: Premarketing Clinical Evaluation, CDER, FDA (2009).

Table 14: Hy's Rule Laboratory Abnormalities

Hepatocellular Injury and Liver Function Tests	Range of Test Values
AST	3 to <5 × ULN
	5 to <10 × ULN
	10 to <20 × ULN
	≥20 × ULN
	>2 × Baseline
ALT	3 to <5 × ULN
	5 to <10 × ULN
	10 to <20 × ULN
	≥20 × ULN
	>2 × Baseline
AST or ALT	3 to <5 × ULN

Hepatocellular Injury and Liver Function Tests	Range of Test Values
	5 to $<10 \times$ ULN
	10 to $<20 \times$ ULN
	$\geq 20 \times$ ULN
	$>2 \times$ Baseline
Total bilirubin	$>$ ULN
	$>1.5 \times$ ULN
	$>2 \times$ ULN
Alkaline phosphatase	$>1.5 \times$ ULN
	$>2 \times$ ULN
AST or ALT plus total bilirubin	$>3 \times$ ULN (AST or ALT) plus $>1.5 \times$ ULN Total Bilirubin, and ALP $<2 \times$ ULN
AST or ALT plus total bilirubin	$>3 \times$ ULN (AST or ALT) plus $>2 \times$ ULN (Total Bilirubin, and ALP $<2 \times$ ULN

ALT = alanine aminotransferase; AST = aspartate aminotransferase; ULN = upper limit of normal

eDISH (evaluation of Drug-Induced Serious Hepatotoxicity) plots will be provided for the maximum AST/ALT post baseline vs the maximum total bilirubin post baseline. Similarly eDISH plots for the maximum AST/ALT post baseline vs the maximum GGT post baseline will be provided.

The mean values and mean change from baseline in GGT, AST, and ALT will be plotted by treatment group over time. The same plots will be generated in units of ULN.

8.3.4. Evaluation of Labs of Special Interest

Liver enzymes (ALT, AST, GGT, ALP) will be evaluated in terms of upper limits of normal (ULN). The result will be divided by the ULN, and summarized using descriptive statistics. In addition, the number and percentage of subjects with GGT or ALP increases $>2\times$, $3\times$, $5\times$, $8\times$, $10\times$, $15\times$, and $20\times$ ULN will be presented based on their maximum post-baseline value, by treatment group.

Summaries of coagulation parameters will be presented by treatment group for the subset of subjects concomitantly taking drugs included in the WHO Drug Dictionary Standardized Drug Grouping “Antithrombotic drugs”.

8.4. Vital Signs

Vital sign results will be listed by treatment, subject, and time point. Vital signs will be summarized using descriptive statistics over time including changes from baseline at each scheduled time point.

8.5. Electrocardiograms

Electrocardiogram results (including heart rate (HR), RR interval, PR interval, QRS duration, QT interval, and QTcF interval will be listed by treatment, subject, and time point. As QTcF could not be calculated on all machines, QTcF will be programmatically derived as QT/RR^(1/3) and used in all summary tables. All data provided on the CRF and derived will be listed.

Electrocardiogram results will be summarized using descriptive statistics over time including changes from baseline at each scheduled time point.

A categorical summary of maximum post baseline QTcF values will be summarized by treatment, in accordance with ICH E14 (Note for guidance on the clinical evaluation of QT/QTc interval prolongation and proarrhythmic potential for non-antiarrhythmic drugs, CHMP/ICH/2/04). The number and percentage of subject with values >450 msec, >480 msec, and >500 msec and increase from baseline values >30 msec and >60 msec.

For any subjects with a QT/QTc/QTcF >500 msec, or QTcF change from baseline of >60 msec, a separate listing of all ECG data for these subjects will be provided.

Abnormal ECG findings will also be listed separately.

8.6. Other Safety Measures

For all of the below ePRO, in cases where the tablets were not working, the data was recorded on paper and transcribed into the EDC. The primary analysis will use all available data (paper and tablet together).

8.6.1. Columbia Suicide Severity Rating Scale (C-SSRS)

The Columbia Suicide Severity Rating Scale (C-SSRS) is provided in protocol Appendix 10. [Table 15](#) describes how to score the C-SSRS and the scoring is done on the CRF. Missing data will not be imputed.

Table 15: C-SSRS Scoring

C-SSRS Item	Derivation
Suicidal Ideation	
A “yes” answer to any one of the following five questions from suicidal ideation section on the C-SSRS.
 
1. Wish to be dead2. Non-specific active suicidal thoughts3. Active suicidal ideation with any methods (not plan) without intent to act4. Active suicidal ideation with some intent to act, without specific plan5. Active suicidal ideation with specific plan and intent 
If a subject answer “yes” to more than one suicidal ideation question within a visit window as an analysis time point, the worst-case response (i.e. the highest) will be used in any summaries.

Suicidal Behavior	
A “yes” answer to any one of the following five questions from suicidal behavior section on the C-SSRS.
 
6. Preparatory acts or behavior7. Aborted attempt8. Interrupted attempt9. Actual attempt10. Completed suicide 
If a subject answer “yes” to more than one suicidal ideation question within a visit window as an analysis time point, the worst-case response (i.e. the highest) will be used in any summaries.

Suicidal Ideation or Behavior	A “yes” answer to any one of the above ten suicidal ideation or behavior questions on the C-SSRS.

C-SSRS Item	Derivation
Self-Injurious Behavior without Suicidal Intent	A “yes” answer to the following question from suicidal behavior section on the C-SSRS: “Has subject engaged in Non-Suicidal Self-Injurious Behavior?”

C-SSRS data will be listed by treatment, subject and visit. Subjects who reported any suicidal ideation and behavior during the main study will also be listed separately.

8.6.2. Hospital Anxiety and Depression Scale (HADS)

The Hospital Anxiety and Depression Score (HADS) is provided in protocol Appendix 11. The HADS is a self-report rating scale of 14 items on a 4-point Likert scale (range 0–3). It is designed to measure anxiety and depression (7 items for each subscale), each item is scored between zero (no impairment) and three (severe impairment). The total score is the sum of the 14 items, and for each subscale the score is the sum of the respective seven items (ranging from 0–21).

The individual Hospital Anxiety and Depression Scale (HADS) items and domain (anxiety and depression) scores will be listed by treatment, subject and visit.

The domain scores and their changes from baseline to maximum post-baseline score will be summarized by treatment group. Domain scores will be categorized as Normal (0-7), Mild Depression (8-10), Moderate Depression (11-15), and Severe Depression (16-21). Summaries will present the number and percentage of subjects with shifts in categories from baseline to maximum post-baseline score by treatment group. Denominators for percentages will be the number of subjects with non-missing data post-baseline and baseline.

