2.3. Benefit/Risk Assessment

Summaries of findings from both clinical and nonclinical studies conducted with rodatristat ethyl as well as more detailed information about the known and expected benefits and risks and reasonably expected adverse events (AEs) of rodatristat ethyl may be found in the Investigator's Brochure. This section outlines the potential adverse events of special interest (AESI; based either on preclinical or clinical data generated to date, the mechanism of action of rodatristat ethyl, or the prescribing information for telotristat ethyl [a TPH inhibitor previously approved for the treatment of carcinoid syndrome-related diarrhea] and mitigation strategies for this protocol. The potential risk for QTc prolongation (described in the Investigator's Brochure) will be further evaluated in a definitive thorough QT study in the future. Until further data are available in that regard, cardiac arrhythmia, related to an increase in QT/QTc interval, will be treated as a potential AESI and has therefore also been included in the table of potential risks below.

Although any potential benefits to patients with PAH will not be known until the study is completed, the development of a drug with disease-modifying potential will certainly be of value to patients with this diagnosis.

Potential Risk	Mitigation Stra	itegy
	Impact on Eligibility	Monitoring and Stopping Criteria OR Management Criteria
Severe constipation	None	Severe constipation (e.g., obstipation with manual evacuation indicated) and/or severe, persistent, or worsening abdominal pain would warrant withdrawal from the study.
Depression/other mood-related disturbance due to central depletion	 Exclusion of patients with active suicidal thinking or behavior at Screening/Baseline based on the Columbia-Suicide Severity Rating Scale (C-SSRS) Exclusion of patients with severe depression at Screening/Baseline based on the Quick Inventory of Depressive Symptoms Clinician-Rated (QIDS-C) or the Hospital Anxiety and Depression Scale (HADS) 	 Withdrawal of patients with: Any significant worsening on postdose C-SSRS indicative of active suicidal ideation with intent to act or suicidal behavior Severe depression or anxiety based on a HADS Depression or Anxiety Score ≥ 15 or a QIDS-C Total Score ≥ 16. Any severe psychiatric or CNS AE as determined by the Investigator.

Protocol RVT-1201-2002 Effective: 19JAN2022

Potential Risk	Mitigation Stra	ntegy

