- 12. End stage renal disease defined as receiving peritoneal dialysis, hemodialysis, or status after renal transplantation, or severe liver disease defined as Child-Pugh Class C, with or without cirrhosis
- 13. Known congenital LQTS or known family history of LQTS
- 14. Depression that is currently rated as severe (defined as a score of ≥ 16 on the QIDS-C and/or [HADS] Depression and/or Anxiety score ≥ 15), recent suicidal behavior (either preparatory acts/behavior, aborted attempt, interrupted attempt, or actual attempt in the past 3 months per the Screening C-SSRS), or active suicidal ideation with intent to act (defined as C-SSRS category score of 4 or 5 in the past month)
- 15. Patients with (during Screening):
 - a. Severe hypertension (SBP > 180 mmHg and/or Diastolic Blood Pressure [DBP] > 110 mmHg), and patients with severe hypotension (SBP < 90 mmHg and/or DBP < 50 mmHg)
 - b. Hypertension or hypotension considered not controlled in line with clinical standards
- 16. Clinically significant electrolyte abnormality (e.g., hypokalemia, hypomagnesemia, or hypocalcemia) in the judgement of the Investigator
- 17. Current or prior history within the last 5 years of neoplasm (except for treated basal cell or squamous small cell carcinoma of the skin with no evidence of recurrence)

18. Any concurrent clinically significant medical condition/disorder which in the Investigator's opinion would interfere with the patient's ability to comply with or complete the study or could affect the interpretation of the efficacy and safety variables.

Protocol RVT-1201-2002

Effective: 19JAN2022

Prior/Concomitant Therapy

- 19. Use of any of the following medications or supplements within 30 days prior to Screening:
 - monoamine oxidase inhibitors (MAOIs; Appendix 1)
 - 5-hydroxytryptophan (5-HTP) or L-tryptophan
 - telotristat ethyl
- 20. Patients currently taking one or more drugs known to prolong the QT interval and which are clearly associated with a known risk of Torsades de Pointe (see Appendix 1)

Diagnostic Assessments

- 21. Estimated glomerular filtration rate (eGFR) < 30 mL/min/1.73 m² at Screening
- 22. 12-Lead ECG results at Screening demonstrating QTcF interval > 450 ms for males or > 470 ms for females
- 23. Elevated ALT, AST, or TBL > 2X ULN
- 24. Any ECG or clinical laboratory abnormality which precludes safe participation in the study in the opinion of the Investigator

Lifestyle

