8.1. Discontinuation of Investigational Product

The Medical Monitor should be notified of any change to background PAH therapy to determine any need for withdrawal. See Section 8.2 for study withdrawal procedures.

Patients meeting any of the following liver chemistry criteria must be withdrawn (IP should be discontinued immediately) from the study by the Investigator:

- ALT or AST > 3X ULN and TBL > 1.5X ULN or INR > 1.5
- ALT or AST > 3X ULN with the appearance of fatigue, nausea, vomiting, right upper quadrant pain or tenderness, fever, rash, and/or eosinophilia (> 5%)
- ALT or AST > 5X ULN for more than 2 weeks
- ALT or AST >8X ULN

If liver chemistry tests meet any of the above criteria, repeat testing should be performed within 48 to 72 hours and the patient followed until resolution.

Patients meeting any of the following confirmed QT/QTc-related criteria must be withdrawn from the study by the Investigator:

- QTcF interval > 500 ms
- QTcF interval > 480 ms AND increase from Baseline ≥ 60 ms
- QTcF interval > 480 ms associated with syncope, life-threatening arrhythmias, resuscitated cardiac arrest, or seizure

The Investigator must also discontinue/withdraw a patient's participation in the study if any of the following criteria apply:

- Pregnancy
- Significant protocol violation/lack of compliance with the study and/or study procedures non-compliance with IP for discontinuation of patient is defined as < 50%.
- Severe constipation (e.g., obstipation with manual evacuation indicated) and/or severe, persistent, or worsening abdominal pain
- Any significant worsening on postdose C-SSRS indicative of active suicidal ideation with intent to act (defined as C-SSRS Suicidal Ideation category score of 4 or 5) or behavior (either preparatory acts/behavior, aborted attempt, interrupted attempt, or actual attempt)
- Severe depression or anxiety based on a HADS Depression or Anxiety score ≥ 15, or a QIDS-C Total Score ≥ 16.

• Any severe psychiatric or CNS AE as determined by the Investigator.

The Investigator may discontinue/withdraw a study patient's participation in the study if any of the following criteria apply:

Protocol RVT-1201-2002

Effective: 19JAN2022

• Behavioral or administrative reason

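### The SAP's HADS shift table classes a score of 15 as moderate, although the protocol treats 15 or more as severe for exclusion and mandatory withdrawal

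*SAP*

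**What the plan says.** SAP 8.6.2 sets the reporting bands for both HADS subscales in one sentence: normal at 0-7, mild depression at 8-10, then "Moderate Depression (11-15), and Severe Depression (16-21"). Each subscale runs from 0 to 21. The bands feed a table of "shifts in categories from baseline to maximum post-baseline score by treatment group". The same section also summarises the domain scores and their change to the maximum post-baseline score, and lists items and domain scores by subject and visit.

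The protocol uses one HADS cut for severe:

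- Section 8.1, among the criteria on which the investigator must discontinue or withdraw the patient: "Severe depression or anxiety based on a HADS Depression or Anxiety score ≥ 15, or a QIDS-C Total Score ≥ 16".
- Section 2.3, in the withdrawal column of the risk table: "Severe depression or anxiety based on a HADS Depression or Anxiety Score ≥ 15 or a QIDS-C Total Score ≥ 16".
- Section 5.2, exclusion 14, as part of its definition of severe: "HADS] Depression and/or Anxiety score ≥ 15". The synopsis repeats this criterion.

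SAP Section 1 says that substantial departures from the protocol's statistical considerations are identified in Section 11. Section 11 does not mention HADS. It has only a general line about added safety analyses.

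**The concern.** The SAP and the protocol both use the word severe for the same score on the same instrument, but start it at different values. A patient withdrawn under protocol 8.1 with a worst score of 15 would be withdrawn for severe depression or anxiety and then tabulated as moderate. Because the output is a shift table, a patient who goes from 11-14 at baseline to a maximum of 15 stays in the moderate band and shows no shift, despite having met a mandatory withdrawal criterion. Similarly, a patient enrolled at 15 contrary to exclusion 14 would appear as moderate at baseline.

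The labels are a second, smaller problem. The categories apply to both domains but all are named as depression, so the anxiety table would carry the wrong label.

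Protocol 9.3.1 includes severe depressive or anxious symptoms in a named adverse event of special interest (AESI). Of the three mood and suicidality instruments, the C-SSRS is planned for listings only (SAP 8.6.1) and the QIDS-C is banded for depression (SAP 8.6.3). The HADS anxiety subscale is thus the only one of these scales that scores anxiety and is summarised by treatment group.

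**Working it through.** No sample size, power or alpha figure lies behind this point, so there is no stated figure to reproduce. The check classifies every possible domain score under both rules.

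**Inputs**

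- SAP 8.6.2: severe if score ≥ 16, moderate if 11 to 15.
- Protocol 2.3, 5.2 and 8.1: severe if Depression or Anxiety score ≥ 15.
- Score range: 0 to 21, giving 22 possible values per domain.

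**Comparison**

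| Domain score | SAP band | Severe under protocol? | Agree on severe vs not severe? |
|---|---|---|---|
| 0-7 | Normal | No | Yes |
| 8-10 | Mild | No | Yes |
| 11-14 | Moderate | No | Yes |
| 15 | Moderate | Yes | **No** |
| 16-21 | Severe | Yes | Yes |

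One value of 22 disagrees. The error has one direction: relative to the protocol definition, the SAP bands can miss a severe case but cannot add one.

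**Size of the shortfall.** For each domain:

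protocol-severe count − SAP-severe count = number of subjects whose maximum post-baseline score is exactly 15.

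A subject who scores 15 at one visit and 16 or more at another is severe under both rules and does not contribute.

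The documents give no frequency for a maximum of exactly 15. As an illustration only, let p be an assumed per-subject probability of that outcome in one domain, with 90 subjects. Expected shortfall = 90p, and the chance of at least one affected subject = 1 − (1 − p)^90.

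| Assumed p | Expected shortfall in 90 | Chance of at least one |
|---|---|---|
| 0.5% | 0.45 | 36% |
| 1% | 0.9 | 60% |
| 2% | 1.8 | 84% |
| 5% | 4.5 | 99% |

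With 30 patients per arm, one such subject is 1/30 = 3.3 percentage points of an arm.

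**Cross-check on the other scale.** The protocol's QIDS-C threshold is 16 or more, and SAP 8.6.3 starts its severe band at 16, so that scale agrees with its withdrawal rule. The HADS boundary between 15 and 16 is the same as the QIDS-C one. It may have been carried across, but that is an inference.

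**If the HADS bands were aligned with the protocol cut** (moderate 11-14, severe 15-21), disagreements would fall from 1 to 0.

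**The case against.** The strongest reply is that the two cuts do different jobs. The protocol's 15 is an eligibility and stopping rule. The protocol specifies no HADS reporting bands, and its section 10.4.3 leaves the HADS analyses to the SAP. Section 11 has to list only substantial differences, and one can argue about whether a one-point band edge qualifies. This is fair as far as it goes, but both documents attach the same word to the cut, and a reader of the safety table will take severe to mean what the protocol says it means.

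Three stronger readings are tempting, and the documents do not support them:

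- **That the AESI summary is wrong.** A reader might take the shift table as the main group summary of the mood AESI. It is not. SAP 8.2.1, Table 12, defines that AESI by MedDRA queries for depression, anxiety and psychosis at Grade 2 or higher, and 8.2.2 and 8.2.3 summarise it by group. HADS scores do not enter that definition.
- **That the table cannot be reconciled with the protocol criterion.** The by-subject listing of domain scores lets anyone count the subjects at 15 or more. Discontinuations with reasons are also tabulated by group (SAP 6.1). What is missing is a ready-made row; the information is there.
- **That severe cases will certainly be undercounted.** This happens only if some subject's maximum is exactly 15.

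It is also true that safety outputs carry no inferential comparison (SAP 8), so no test depends on the cut.

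**Conclusion.** The inconsistency is real and is confined to one score value. As written, the HADS shift table would fall short of the protocol-defined severe count by the number of subjects with a maximum post-baseline domain score of exactly 15, separately for depression and anxiety. That number is unknown and may be zero. The 36% to 99% range rests wholly on an assumed probability of 0.5% to 5% and is not an estimate for this trial. The anxiety labelling error stands whatever the scores turn out to be.

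Nothing else moves: the continuous HADS summaries, the listings, the AESI counts, the patient-level withdrawal rule and all efficacy results are unaffected. This is a minor correction, worth making because it bears on how withdrawals for severe mood symptoms appear in the group tables.

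**What to change.** Reconcile SAP 8.6.2 with protocol 2.3, 5.2 and 8.1. The simplest route keeps the present bands and adds to the shift table a count, by treatment group, of subjects with a post-baseline HADS Depression or Anxiety score meeting the protocol criterion (≥ 15), shown for each domain. The table can then be matched directly to the protocol rule. Alternatives are to align the reporting bands with the protocol threshold, or to keep them and explain the difference in Section 11. In any case, name the anxiety-domain categories as anxiety.

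The cost is about one line of SAP text and one table shell, with no new data. Which clinical threshold is right is for the protocol to state.

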8.6.3. Quick Inventory of Depressive Symptomatology (QIDS)

The clinician-rated Quick Inventory of Depressive Symptomatology (QIDS) is provided in protocol Appendix 12. Total QIDS scores range from 0 to 27 (Rush et al., 2003), with scores of 5 or lower indicative of no depression, scores from 6 to 10 indicating mild depression, 11 to 15 indicating moderate depression, 16 to 20 reflecting severe depression, and total scores greater than 21 indicating very severe depression. The total score is the sum of all item scores. The sleep domain score is the highest score on any one of the four sleep items. The appetite/weight domain score is the highest score on any one of the four appetite/weight items. The psychomotor domain score is the highest score on any one of the two psychomotor items.

The Clinician-Rated Quick Inventory of Depression (QIDS-C) individual items, total and domain scores will be listed by treatment, subject and visit.

The results and change from baseline to maximum post-baseline score in QIDS-C total and domain scores will be summarized by treatment group.

The total score will be categorized as No Depression (0-5), Mild Depression (6-10), Moderate Depression (11-15), Severe Depression (16-20), and Very Severe Depression (21+). Summaries will present the number and percentage of subjects with shifts in categories by treatment group.

Denominators for percentages will be the number of subjects with non-missing data at the specific visit and baseline.

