9.2.8.3. Quick Inventory of Depressive Symptomatology

The 16-item QIDS (Rush et al., 2003) is designed to assess the severity of depressive symptoms. The QIDS is available in the clinician-rated (QIDS-C) and self-reported versions (QIDS-SR). Both versions assess all the criterion symptom domains designated by the American Psychiatry Association Diagnostic and Statistical Manual of Mental Disorders - 4th edition (DSM-IV) (APA, 1994) and the 5th edition adds reference to diagnose a major depressive episode. The QIDS-C version will be used in this study. The QIDS-C is sensitive to change with medications, psychotherapy, or somatic treatments, making it useful for both research and clinical purposes. The psychometric properties of the QIDS-C have been established in various study samples.

An example of the QIDS-C can be found in Appendix 12.

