APPENDIX 12. CLINICIAN-RATED QUICK INVENTORY OF DEPRESSIVE SYMPTOMATOLOGY

NAME:	 TODAY'S DATE:	

Please circle one response to each item that best describes the patient for the last seven days.

- 1. Sleep Onset Insomnia:
 - 0 Never takes longer than 30 minutes to fall asleep.
 - 1 Takes at least 30 minutes to fall asleep, less than half the time.
 - 2 Takes at least 30 minutes to fall asleep, more than half the time.
 - 3 Takes more than 60 minutes to fall asleep, more than half the time.
- 2. Mid-Nocturnal Insomnia:
 - 0 Does not wake up at night.
 - 1 Restless, light sleep with few awakenings.
 - Wakes up at least once a night, but goes back to sleep easily.
 - Awakens more than once a night and stays awake for 20 minutes or more, more than half the time.
- 3. Early Morning Insomnia:
 - 0 Less than half the time, awakens no more than 30 minutes before necessary.
 - 1 More than half the time, awakens more than 30 minutes before need be.
 - 2 Awakens at least one hour before need be, more than half the time.
 - 3 Awakens at least two hours before need be, more than half the time.
- 4. Hypersomnia:
 - O Sleeps no longer than 7-8 hours/night, without naps.
 - 1 Sleeps no longer than 10 hours in a 24 hour period (include naps).
 - 2 Sleeps no longer than 12 hours in a 24 hour period (include naps).
 - 3 Sleeps longer than 12 hours in a 24 hour period (include naps).

Enter the highest score on any 1 of the 4 sleep items (1–4 above) _____

- Mood (Sad):
 - 0 Does not feel sad.
 - 1 Feels sad less than half the time.

Protocol RVT-1201-2002

- 2 Feels sad more than half the time.
- 3 Feels intensely sad virtually all the time.
- 6. Appetite (Decreased):
- 0 No change from usual appetite.
- 1 Eats somewhat less often and/or lesser amounts than usual.
- 2 Eats much less than usual and only with personal effort.
- 3 Eats rarely within a 24-hour period, and only with extreme personal effort or with persuasion by others.
- 7. Appetite (Increased):
 - 0 No change from usual appetite.
 - 1 More frequently feels a need to eat than usual.
 - Regularly eats more often and/or greater amounts than usual.
 - 3 Feels driven to overeat at and between meals.
- 8. Weight (Decrease) Within The Last Two Weeks:
 - 0 Has experienced no weight change.
 - 1 Feels as if some slight weight loss occurred.
 - 2 Has lost 2 pounds or more.
 - 3 Has lost 5 pounds or more.
- 9. Weight (Increase) Within the Last Two Weeks:
 - 0 Has experienced no weight change.

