 - Feels as if some slight weight gain has occurred.
 - 2 Has gained 2 pounds or more.
 - 3 Has gained 5 pounds or more.

Enter the highest score on any 1 of the 4 appetite/weight change items (6–9 above)

10. Concentration/Decision Making:

- 0 No change in usual capacity to concentrate and decide.
- 1 Occasionally feels indecisive or notes that attention often wanders.
- 2 Most of the time struggles to focus attention or make decisions.
- 3 Cannot concentrate well enough to read or cannot make even minor decisions.

11. Outlook (Self):

- O Sees self as equally worthwhile and deserving as others.
- 1 Is more self-blaming than usual.
- 2 Largely believes that he/she causes problems for others.
- 3 Ruminates over major and minor defects in self.

12. Suicidal Ideation:

- 0 Does not think of suicide or death.
- 1 Feels life is empty or is not worth

living.

- Thinks of suicide/death several times a week for several minutes.
- 3 Thinks of suicide/death several times a day in depth, or has made specific plans, or attempted suicide.

13. Involvement:

- 0 No change from usual level of interest in other people and activities.
- 1 Notices a reduction in former interests/activities.
- 2 Finds only one or two former interests remain.
- 3 Has virtually no interest in formerly pursued activities.

14. Energy/Fatiguability:

0 No change in usual level of energy.

Protocol RVT-1201-2002

Effective: 19JAN2022

- 1 Tires more easily than usual.
- 2 Makes significant personal effort to initiate or maintain usual daily activities.
- 3 Unable to carry out most of usual daily activities due to lack of energy.

15. Psychomotor Slowing:

- Normal speed of thinking, gesturing, and speaking.
- 1 Patient notes slowed thinking, and voice modulation is reduced.
- 2 Takes several seconds to respond to most questions; reports slowed thinking.
- 3 Is largely unresponsive to most questions without strong encouragement.

16. Psychomotor Agitation:

- No increased speed or disorganization in thinking or gesturing.
- 1 Fidgets, wrings hands and shifts positions often.
- 2 Describes impulse to move about and displays motor restlessness.
- 3 Unable to stay seated. Paces about with or without permission.

Protocol RVT-1201-2002 Effective: 19JAN2022

Enter the highest score on either of the 2 psychomotor items (15 or 16 above) _____

Scoring	Interpretation	
Enter the highest score on any 1 of the 4 sleep items (1 – 4)	 Normal	0 – 5
Item 5	 Mild	6 – 10

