Enter the highest score on any 1 appetite / weight item $(6-9)$	 Moderate	11 – 15
Item 10	 Severe	16 – 20
Item 11	 Very Severe	21+
Item 12		
Item 13		
Item 14		
Enter the highest score on either of the 2 psychomotor items (15 and 16)		
Total Score (Range 0 – 27)	 LIT Cavithava atawa Madisal (

^{© 1986, 2000} UT Southwestern Medical Center, Dallas

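### SAP 8.6.3 defines the QIDS-C total as the sum of all items, which contradicts its own 0–27 range and the nine-component scoring in protocol Appendix 12

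*SAP*

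**What the plan says.** SAP 8.6.3 refers to protocol Appendix 12 for the instrument and states "Total QIDS scores range from 0 to 27". It then gives the derivation: "The total score is the sum of all item scores". The next three sentences define sleep, appetite/weight and psychomotor domain scores, each as the highest item in its group. They do not say that these domain scores replace their items in the total. Items, total and domain scores are named as separate outputs. The total is sorted into bands of 0–5, 6–10, 11–15, 16–20 and 21+, and category shifts are tabulated by treatment group.

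Protocol 9.2.8.3 describes "The 16-item QIDS". Appendix 12 prints each item with options 0 to 3. For the sleep group its instruction is "Enter the highest score on any 1 of the 4 sleep items", with matching instructions for appetite/weight (items 6–9) and psychomotor (items 15–16). Its scoring box has nine lines and ends with "Total Score (Range 0 – 27".

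SAP Section 11, which lists changes from the protocol's planned analyses, mentions no change to QIDS-C scoring.

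**The concern.** A derivation rule in an SAP is what the programmer codes, and this one does not produce the range printed a few lines above it. The bands are calibrated to a total of at most 27. Applied to a sum over 16 items, they would label some patients as more depressed than the form does.

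The surrounding text makes a literal reading easy. SAP 8.6.2 defines the HADS total as a plain sum of its 14 items, where a plain sum is meant. SAP 8.6.1 says that C-SSRS scoring is done on the CRF; 8.6.3 says nothing similar, so the QIDS-C total may well be computed from items. SAP Section 1 also says that the SAP supersedes the protocol's statistical considerations.

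At stake are the mood-safety tables. Protocol 5.2 and 8.1 use a QIDS-C score of 16 or more as an exclusion and a withdrawal criterion. Inflated totals could list patients at 16 or above who never reached that score on the site's form, and they would look like eligibility deviations or missed withdrawals.

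**Working it through.** **Inputs.** Sixteen items (protocol 9.2.8.3), each scored 0–3 (Appendix 12). Grouping from Appendix 12: sleep, items 1–4; appetite/weight, items 6–9; psychomotor, items 15–16; single items 5, 10, 11, 12, 13 and 14. Bands from SAP 8.6.3.

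**Reproducing the stated range.** Appendix 12 total = max(1–4) + item 5 + max(6–9) + items 10 to 14 + max(15–16). That is 3 domain maxima + 6 single items = 9 components, and 9 × 3 = 27. This matches the range in both documents.

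**The SAP sentence taken literally.** Total = sum of items 1 to 16, so the maximum is 16 × 3 = 48. The surplus of 21 comes from sleep (12 − 3 = 9), appetite/weight (12 − 3 = 9) and psychomotor (6 − 3 = 3). If nobody scores both directions of appetite or both directions of weight, the maximum is 48 − 6 = 42. If insomnia with hypersomnia is also ruled out, it is 42 − 3 = 39. None of these is 27.

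**Direction.** Literal total minus Appendix 12 total is (sum − max), added over the three multi-item domains. Each term is zero or positive, so a total is never lowered. Each term is zero when at most one item in the domain is above 0.

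**Worked patterns, items 1–16:**

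| Items | Appendix 12 | Literal sum |
|---|---|---|
| 2,2,2,0,1,2,0,2,0,1,1,0,1,1,1,1 | 2+1+2+4+1 = 10, mild | 6+1+4+4+2 = 17, severe |
| 2,2,2,0,2,2,0,2,0,1,1,0,2,2,1,1 | 2+2+2+6+1 = 13, moderate | 6+2+4+6+2 = 20, severe |
| 2,0,0,0,1,1,0,0,0,1,0,0,1,1,1,0 | 2+1+1+3+1 = 8, mild | 2+1+1+3+1 = 8, mild |

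The terms are sleep, item 5, appetite/weight, items 10–14 and psychomotor. No pattern pairs insomnia with hypersomnia or opposite appetite or weight changes.

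**Lowest true score that can reach 16.** With such pairings excluded, a true total of 6 reaches at most 3×3 + 2×3 = 15. A true total of 7 (sleep 3, appetite/weight 3, psychomotor 1) reaches 9 + 6 + 2 = 17.

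**Change scores.** The error in a change is the surplus after baseline minus the surplus at baseline, so it can go either way. A patient with the first pattern at baseline and the third afterwards changes by 8 − 10 = −2 by Appendix 12 and by 8 − 17 = −9 by the literal sum.

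**Share affected.** The documents give no item distributions. As an illustration only, items were simulated with assumed probabilities of a zero score between 45% and 75% and latent correlations of 0.2 or 0.5, giving mean true totals of about 4 to 10. Between 7% and 60% of assessments moved up at least one band, and 1% to 25% crossed from below 16 to 16 or above. With contradictory answers excluded, the upper ends fell to about 30% and 11%. The width of these ranges shows that the share is not determined.

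**The case against.** The best defence is that the paragraph resolves itself. It points to Appendix 12, prints 0 to 27, uses bands that fit that range and gives the highest-item rules directly after the disputed sentence. Only the nine-component total satisfies all of these. A careful programmer would see that, and any literal total above 27 would expose the mistake. Items and domain scores are also listed, so the correct total can be recomputed from the reported data. This all stands, and it limits the point to a contradiction that does harm only if the sentence is coded as written. It does not make the sentence right: most inflated totals would lie within 0–27 and raise no alarm, as 17 and 20 do above.

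A reader might infer three stronger things that the documents do not support.

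- **That patients in general are pushed into the severe bands.** Some can be, but sparse patterns do not move at all, and others move only to mild or moderate.
- **That withdrawals are affected.** Under protocol 8.1 the investigator applies the threshold of 16 during the study, to a clinician-rated form that carries the correct rule. The SAP derivation plays no part in that.
- **That counts of adverse events of special interest are affected.** SAP 8.2.1 defines the mood category by MedDRA queries for depression, anxiety and psychosis at Grade 2 or above. The QIDS-C total is not an input.

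**Conclusion.** The sentence is wrong as written: it contradicts the range and bands beside it and the instrument it cites. With no scoring change listed in Section 11, it reads as a drafting slip and not as a chosen alternative.

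Its size is an arithmetic maximum of 48 against 27, with individual totals raised by anything from 0 to 21 points and possible moves of one or more bands. This rests on two assumptions: that the total is computed from items and not taken from the completed form, and that the sentence is coded literally. The number of patients who would change band cannot be stated from the documents.

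The reach is limited to the descriptive QIDS-C total, its change from baseline and the category shift tables. SAP Section 8 plans no inferential comparison of safety endpoints, and the efficacy analyses, power and error control are untouched. It should be corrected because the tables concern a named safety interest and the correction is nearly free.

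**What to change.** Replace the sentence in SAP 8.6.3 with: total = sleep domain (highest of items 1–4) + item 5 + appetite/weight domain (highest of items 6–9) + items 10 to 14 + psychomotor domain (higher of items 15–16), range 0–27, as in protocol Appendix 12. State as well whether the total is derived from items or taken from the form; if it is derived, compare it with the form's total where one was recorded.

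In the same edit, align the wording for the top band. The text puts very severe above 21 while the category list starts it at 21, so a score of exactly 21 has no band in the text.

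The cost is one or two sentences in the SAP and a check of the derivation program. No data collection, clinical rule or other analysis changes.
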